## IRB Minimal Risk Protocol Template

**Note: If this study establishes a human specimen repository (biobank) for research purposes, do not use this template. Use the Mayo Clinic Human Specimen Repository Protocol Template found on the IRB home page under Forms and Procedures at <http://intranet.mayo.edu/charlie/irb/>**

**First-time Use:** Use this template to describe your study for a new IRB submission.

1. Complete the questions that apply to your study.
2. Save an electronic copy of this protocol for future revisions.
3. When completing your IRBe application, you will be asked to upload this document to the protocol section.

**Modification:** To modify this document after your study has been approved:

1. Open your study in IRBe. Click on the study 'Documents' tab and select the most recent version of the protocol. Save it to your files.
2. Open the saved document and activate "Track Changes".
3. Revise the protocol template to reflect the modification points , save the template to your files
4. Create an IRBe Modification for the study and upload the revised protocol template.

### Research Question and Aims

Hypothesis: Can our team develop a potentially groundbreaking means of delivering sound that could change the way in which hearing care professionals can deliver hearing intervention as well as the way immersive reality systems communicate sound.

Aims, purpose, or objectives:

1. Develop a portable wearable hardware headset using a computer-based software that can establish the optimal stimulation parameters appropriate for medical and consumer environments for individuals with hearing impaired and normal hearing individuals.
2. Incorporate a noise cancellation technology for the cochlear system
3. Establish speech intelligibility above 90% for normal hearing individuals in quiet and 8/10 satisfaction of music.
4. Develop a surround sound system for entertainment and media

**Background (Include relevant experience, gaps in current knowledge, preliminary data, etc.):**

Noninvasive electrostimulation of the cochlea has notable benefits for normal hearing and hearing-impaired individuals that extend well-beyond conventional acoustic and bone conducted enhancements of sound. Although the technique has been known since the 19th century little clinical attention or application of the technique has occurred, particularly related to a wearable technology for individual use. The present project will gather experts in the fields of clinical audiology, engineering, and acoustics to design and develop a wearable amplification device with the capability of an extended high frequency range for improved fidelity, directionality, noise cancellation, and surround sound. The markets targeted with this technology span the domains of hearing amplification, noise reduction, and entertainment and media.

Initial studies for an Army funded grant in 2019 showed excellent speech intelligibility in quiet and noise. The technology had the limitations of a single channel of stimulation reducing directionality, non-portability, and a reduced dynamic range of amplification. With the design and development of a new head worn system all the major limitations will be addressed widely enhancing the benefit to users and the markets they represent. [REDACTED]

[REDACTED]

The conventional transmission of sound is through air and bone conduction. Acoustic receivers and bone conduction transducers offer the capability to enhance hearing for a variety of uses in the world of sound. However, there is another approach to create the perception of sound that is largely ignored despite its notable and unique capabilities. Auditory electrostimulation has been known since the early 1800's when it was shown that electrical energy fields applied to the skin could create the perception of sound. Well known 19th century physicists, Volta and Fechner, experimented with "neurophonic hearing" to create a perception of sound. In the 1970's scientists discovered that the perception of sound could also be created through an electrode system with amplitude modulated electromagnetic signals to stimulate the cochlea directly.

A new technique of electrostimulation utilizes an audio signal to modulate a high frequency carrier wave (60 to 80 kHz) (Tonndorf and Kurman, 1984; Cevette et al, 2019). The combined signals are transmitted to the listener through pairs of externally applied electrodes at or near the head. The striking result is the perception by the listener of extremely high-fidelity broad-spectrum signals, ranging up to 20,000 Hz, without involvement of traditional acoustic transducers or the influence of the outer and middle ear structures. Because multiple pairs of electrodes are possible notable directionality using time and level of current through lateralization can create a surround sound experience. The outcome of this capability is a new product that addresses complex problems in hearing abnormalities inadequately addressed with conventional hearing devices by by-passing outer and middle ear structures and overcoming the limitations of currently available frequency ranges. The capability to provide localization of sound enhances the hearing experience for those individuals unfortunate to have asymmetrical hearing loss and single-sided deafness (SSD).

In 2019 the Aerospace Medicine and Vestibular Research Laboratory (AMVRL) and Vivonics won an award from the Department of Defense to use our technique to investigate whether we could provide a very high degree of speech intelligibility in quiet and extreme background noise (95 dB SPL) using our cochlear stimulation system. The military is interested in alternate modes of communication that will provide better

security in field applications. AMVRL successfully provided the benefits required by the Army by showing that through a one channel electrode array we were able to achieve 95.6% word recognition ability in quiet and 84.4% in the presence in a high noise level using appropriate ear protection. The non-portable system employed was fixed hardware instrumentation tethered to an electrical source.

The Mayo Clinic team has a long history of taking an idea from conception to commercialization. Over the past 15 years the team has completed a variety of topics but with notable development using galvanic vestibular stimulation (GVS) integrated with flight simulation to enhance training fidelity and reduce the reduction of simulator sickness [REDACTED] and the HearHook

## Preliminary Results

The Mayo Clinic/Vivonics team demonstrated that speech could be delivered to the subject through the skin electrodes in a manner that allowed the subject to recognize 95.6% in quiet and 84.4% in extreme noise of the words in a 50 word Modified Rhyme Test (MRT). Additionally, a small battery powered breadboard prototype was developed demonstrating that the system was capable of being transformed into a portable system, which will be used to optimize the system prior to full miniaturization. Given these results, the team considers this initial effort highly successful and is the first step to realizing a potentially groundbreaking means of delivering sound that could change the way in which hearing care professionals can deliver hearing intervention as well as the way immersive reality systems communicate sound. The ability to lateralize electroacoustic sound with different electrode placement in conjunction with forehead bone conduction is shown in the Figure 1 below. The blue highlighted areas represent where the sound was perceived under the various conditions creating a pathway for surround sound with a multiple electrode array.

[figure not shown]

[figure not shown]
Figure 1. Lateralization plots by electrode placement using forehead bone conduction.

### **Key Objectives**

[figure not shown]
1. Leverage the promising preliminary results with the overall objective to fully characterize the non-invasive cochlear stimulation system with multiple inputs and finalize concepts.
2. Based on the feedback from the initial study with the Army the team at Vivonics shall upon direction from Mayo Clinic upgrade, test, and demonstrate a benchtop system optimized for clinical studies.
3. Conduct comprehensive clinical trials that include amplitude requirements, threshold and suprathreshold studies, lateralization, and word recognition with 30 participants.
4. Integrate electrode inputs with multimicrophone noise cancellation.
5. Finalize systems with universal headset.
6. Conduct clinical trials integrating noise cancellation in the context of word recognition and lateralization for 20 normal hearing, 20 bilateral sensorineural, and 20 single-sided deafness participants

Specific Objectives	Quarter after Award								Responsible
	1	2	3	4	5	6	7	8	
1. Gather inputs and Finalize Concepts	■								Mayo and Vivonics
2. Optimize Clinical System	■	■	■						Mayo and Vivonics
3. Execute technology characterization study (n=30)	■	■	■	■	■				Mayo Clinic
4. Integrate electrode inputs with microphone array				■	■				MCK and Vivonics
5. Finalize systems with universal headset clinical trial					■	■	■		Mayo Clinic
6. Prepare technology for commercialization						■	■		Mayo Clinic

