### First phase clinical trial:

1) 30 normal hearing participants will be recruited to measure amplitude, threshold, lateralization, and speech intelligibility using the prototype compared to conventional acoustic measures.

2) Parameters for electrode interaction between two channels of electrical stimulation by level of current and timing will be measured in the same participant pool.

3) Algorithms will be established for surround sound based upon the electrode interaction data.

Subjects will be seated in a comfortable chair in a sound treated test room (100dB of attenuation from outside sound). Standard insert earphones and surface electrodes will be used in acoustic and electrostimulation respectively. Acoustic signals will be generated by a standard diagnostic audiometer used in hearing evaluations. Electroacoustic signals will be generated by the Vivonics programmable prototype. The participant will respond to the auditory signals to indicate the lowest level of perception, the location of the signal within the head, and word recognition using a standard work recognition test.

Second phase clinical trial:

1) 15 bilateral hearing impaired, and 15 asymmetrical hearing-impaired participants will be recruited to evaluate directionality of the surround sound system for speech and music,

2) 30 normal hearing participants will be recruited to implement amplitude adjustments to offset simulated cochlear hearing loss with narrowband masking noise and compare the findings to standard acoustic measures of threshold and speech recognition.

Subjects will be seated in a comfortable chair in a sound treated test room (100dB of attenuation from outside sound). Standard insert earphones, bone conduction, and surface electrodes will be used in acoustic and electrostimulation respectively. Acoustic signals will be generated by a standard diagnostic audiometer and bone conduction used in hearing evaluations. Electroacoustic signals will be generated by the Vivonics programmable prototype. The participant will respond to the auditory signals to indicate the lowest level of perception, the location of the signal within the head, and word recognition using a standard work recognition test.

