Standard clinical narrowband masking noise will be used to simulate hearing loss and assess the suprathreshold perception of electric signals. Narrowband masking noise will be introduced via earphones and will be presented at suprathreshold levels between 25-50 dB HL at all frequencies. The masking noise of a maximum of up to 50 dB HL is below than the sound levels categorized as “loud sound (> 85 dB SPL). In fact, the sound levels of normal speech are around 60 dB SPL. While this is occurring, the skin electrodes will be used as reported above, and the perception of the threshold will be evaluated with the addition of masking noise. This is to simulate a higher hearing threshold and assess if the electric signal can still be heard over the masking noise. This protocol is to further develop the modeling from the first phase that will be used to predict electric thresholds using air conduction threshold inputs.

In the second phase 8-space will be utilized which is an 8-speaker system that provide independent sound source as an evaluation of localization. The localization experiment will include electrostimulation data from the first phase in combination with a prototype multi-microphone headset to evaluate the necessary parameters for precise localization for bilateral, unilateral, and normal hearing participants. A signal-to-noise ratio of various levels will be adjusted to evaluate the efficacy of the noise cancellation system developed by MCK Audio. Participants will be asked to rate the quality of music of the electroacoustic system on a 1-10 scale.

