**Third phase clinical trial:**

- 1) 30 normal hearing participants will be recruited to evaluate parameters of electrical stimulation for body-worn electrodes. Laterality and amplitude measures will be assessed for tone and speech stimuli.
- 2) All of the methods used in Phase 3 have been previously described and approved for Phases 1 and 2, with the difference lying in where the electrodes are placed on the body for Phase 3.

Following informed consent, the investigators will evaluate the auditory perception and magnitude of electrical stimulation at the wrist, forearm, and base of the neck by comparing the responses to those established at the forehead, mastoids, and neck. Each threshold from 250Hz through 20 KHz will be determined with a method of limits approach for both acoustic and electrostimulation. Once these thresholds are established, then we will test speech recognition at these distal locations by measuring percent correct in MRT testing at a suprathreshold level.

Of primary interest is the assessment of lateralization of sound when the electrodes are placed on the wrist, forearm, and back by employing unique channels of electrostimulation to determine the place and degree of separation of sound compared to the traditional lateralization of ear-to-ear with traditional acoustic hearing. Participants will have electrodes affixed to the three locations on their body (wrist, forearm, and base of the neck), and a matrix of possible combinations will be tested for perception threshold and location. At each test point, the perception threshold will be evaluated by increasing the amplitude of the current input until the subject can hear a tone. The location of the sound will be recorded on the three-dimensional spherical plot.

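### Key Objective 6 plans 20 bilateral and 20 single-sided-deafness participants, but the second-phase methods recruit 15 bilateral and 15 asymmetrical, apparently for the same trial

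*Protocol*

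**What the plan says.** Key Objectives, item 6, describes a trial of noise cancellation, word recognition and lateralization in "20 normal hearing, 20 bilateral sensorineural, and 20 single-sided deafness participants". It does not say which phase this is.

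The methods name three phases:

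- **First phase:** "30 normal hearing participants will be recruited to measure amplitude, threshold, lateralization, and speech intelligibility using the prototype". No impaired participants are mentioned.
- **Second phase, item 1:** "15 bilateral hearing impaired, and 15 asymmetrical hearing-impaired participants will be recruited to evaluate directionality of the surround sound system". Item 2 adds: "30 normal hearing participants will be recruited to implement amplitude adjustments to offset simulated cochlear hearing loss with narrowband masking noise". The text that follows uses varying signal-to-noise ratios to "evaluate the efficacy of the noise cancellation system developed by MCK Audio", and describes a localization experiment to find the "necessary parameters for precise localization for bilateral, unilateral, and normal hearing participants".
- **Third phase:** "30 normal hearing participants will be recruited to evaluate parameters of electrical stimulation for body-worn electrodes". Again no impaired participants are mentioned.

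Subject Information gives a target accrual of 100, broken down as 30, 60 and 30 for the three phases. Its only inclusion criterion is an age range, so it does not define the hearing groups.

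**The concern.** Group sizes and group definitions are what a site recruits to. Two current sections of the protocol give different ones for what appears to be the same trial. A site following the methods would enrol fewer impaired participants than item 6 plans.

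The one-sided group also changes name: single-sided deafness in item 6, asymmetrical in the second-phase recruitment list, and unilateral in the second-phase localization text. The Background says that localization would help "those individuals unfortunate to have asymmetrical hearing loss and single-sided deafness (SSD"), which names the first two as separate conditions. A group recruited as asymmetrical need not contain many single-sided-deaf participants, or any. A conclusion about single-sided deafness could then rest on few such people or none.

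**Working it through.** **Step 1. Is it the same trial?** The evidence for the link:

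- Item 3 of the Key Objectives (30 participants; threshold, lateralization and word recognition) corresponds to the first phase, so item 6 should be a later trial.
- The first and third phases each recruit 30 normal-hearing participants and nobody else. Only the second phase enrols impaired participants.
- Noise-cancellation testing is described only in the second phase.
- Item 6 totals 20 + 20 + 20 = 60. The second phase totals 30 + 15 + 15 = 60. Both reproduce the phase 2 figure of 60 in Subject Information.

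Because both splits give 60, the accrual figure supports the link but cannot show which split governs.

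**Step 2. Compare the groups.**

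| Group | Key Objective 6 | Second-phase methods | Difference |
|---|---|---|---|
| Bilateral | 20 | 15 | −5 (−5/20 = −25%) |
| One-sided | 20 (single-sided deafness) | 15 (asymmetrical) | −5 (−5/20 = −25%) |
| All impaired | 40 | 30 | −10 (−10/40 = −25%) |
| Normal hearing | 20 | 30 | +10, but recruited for a different task |

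The bilateral label also differs: item 6 restricts it to sensorineural loss and the second phase does not.

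**Step 3. Effect on precision.** Assume the same standard deviation under either plan. The standard error of a group mean is then proportional to 1/√n, and √(20/15) = 1.155. A group of 15 has a standard error about 15% larger than a group of 20. The protocol gives no standard deviation, so this is only a ratio.

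**Step 4. Single-sided-deaf participants.** Item 6 plans 20. The second phase states no number. If some or all of its asymmetrical group may have single-sided deafness, the number lies between 0 and 15. That is a logical bound, not a forecast.

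**Step 5. Accrual total.** 30 + 60 + 30 = 120, against a stated 100, a gap of 20. The three phase figures agree with the recruitment numbers in the methods: 30, then 15 + 15 + 30 = 60, then 30. The total of 100 is the outlier.

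**The case against.** **Item 6 may be a separate, later trial.** It follows an item on finalizing the universal headset, and the timetable has a row for a clinical trial of that headset. The second phase uses a prototype and stresses directionality and simulated loss. This reading is possible, so the link must stay an inference. It does not remove the problem: item 6 would then be a 60-person trial with no methods and no place in the accrual line. An edit is needed either way.

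**The methods plainly govern.** The Key Objectives precede Study Design and Methods and read as an award work plan, whereas the methods say who will be recruited. This largely stands. It points to the simplest correction, but it does not make the two texts agree.

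**The normal-hearing comparison mixes tasks.** This stands. A reader might infer that all three groups conflict equally. The documents do not support that, because the 30 are recruited for the masking task. The localization text includes normal-hearing participants but gives no number for them.

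**The one-sided label is only wording.** The Background sentence describes potential benefit and does not define study groups. That is fair, but the protocol defines these groups nowhere, so the label is all a recruiter has.

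**Nothing statistical depends on the split.** This stands. The power statement is marked not applicable, and the stated endpoints are device deliverables.

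**Conclusion.** The inconsistency is real and should be fixed. Its firm content is 20 against 15 in each impaired group, 40 against 30 overall (25% fewer), and a one-sided population that carries three names. It rests on the inference that item 6 and the second phase are the same trial, which the text supports well but never states.

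Two stronger readings are not supported:

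- A reader might infer from the accrual line that the phase 2 figure of 60 is itself in doubt, or that only 100 − 30 − 30 = 40 places remain for that phase. The second-phase recruitment numbers give 60 independently, and the methods confirm 30 for each of the other phases. The error lies in the total, unless participants are shared between phases, which the protocol does not say.
- A reader might infer that the conflict undermines a sample-size justification or a planned test. The protocol states neither a power calculation nor an endpoint that depends on the split.

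**What to change.** 1. Reconcile Key Objective 6 with both second-phase texts (the recruitment list and the localization paragraph), giving one phase 2 allocation by group and number. Since the methods state who will be recruited, the simplest edit is to restate item 6 as 30 normal-hearing, 15 bilateral and 15 one-sided. If 20/20/20 is intended, change the second-phase recruitment list instead. State which phase item 6 refers to.
2. Use one name and one population for the one-sided group in all three places. Limit any conclusion about single-sided deafness to participants who have it.
3. In the same edit, correct the Subject Information total to 120, or state that participants may serve in more than one phase.

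The cost is wording only, with no new procedure. If 20/20/20 is chosen, recruitment moves from the current methods by 10 more impaired participants (40 − 30) and 10 fewer with normal hearing (30 − 20), and the phase 2 total stays at 60.

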**Collaborators:**

## Study Design and Methods

**Methods:** *Describe in lay terms, completely detailing the research activities that will be conducted by Mayo Clinic staff under this protocol.*

Following informed consent Mayo Clinic staff will evaluate the auditory perception of electrical stimulation by comparing the responses to traditional audiological threshold measures and word recognition. Each threshold from 250Hz through 20 KHz will be determined with a method of limits approach for both acoustic and electrostimulation. Once these thresholds are established then we will measure percent correct in standardized word recognition testing using isophonemes and words at a suprathreshold level of 60dB HL.

Of primary interest is the assessment of lateralization of sound within the head by employing 4 channels of electrostimulation to determine the place and degree of separation of sound compared to the traditional lateralization of ear-to-ear with traditional acoustic hearing. These measures will be conducted by changing the level and timing of current between electrode pairs. Given there are four electrode pairs we will establish the critical parameters for timing and current that yield specific patterns of lateralization. Data will be recorded on a spherical plot representing perception within the head.

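### Word recognition is fixed at 60 dB HL and called suprathreshold, which is untrue for any hearing-impaired ear tested in Phase 2 whose threshold is 60 dB HL or worse

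*Protocol*

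**What the plan says.** The general Methods (Protocol, Study Design and Methods) measure pure-tone thresholds first, acoustically and electrically, and then turn to words, where the plan is to "measure percent correct in standardized word recognition testing using isophonemes and words at a suprathreshold level of 60dB HL". This is a single absolute level. It is not limited to a phase or a hearing group, and it is not tied to the thresholds just measured.

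The Second phase clinical trial states that "15 bilateral hearing impaired, and 15 asymmetrical hearing-impaired participants will be recruited", alongside 30 normal-hearing participants. Its procedure paragraph lists what the participant will report, ending with "the location of the signal within the head, and word recognition using a standard work recognition test". It makes no exception for the hearing-impaired groups and gives no level of its own. Key Objectives, item 6, likewise plans trials of noise cancellation in the context of "word recognition and lateralization for 20 normal hearing, 20 bilateral sensorineural, and 20 single-sided deafness participants".

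Subject Information admits participants by age, 21 to 75. The exclusions that concern hearing are cochlear implants and fluctuating sensorineural loss. No degree of loss is excluded.

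The Third phase clinical trial, which enrols normal-hearing participants only, asks for a suprathreshold level without attaching a number.

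**The concern.** Suprathreshold is a relative property: it depends on the ear. A level of 60 dB HL is absolute. The two agree only when the tested ear's threshold is below 60 dB HL. That is safe for normal hearing, but the protocol also enrols people with hearing loss of any degree and names single-sided deafness as a target.

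The interpretation of the acoustic word score is at stake. The Methods judge electrical stimulation against conventional threshold and word-recognition measures. If words are presented at or below an ear's threshold, a low score may mean that the listener recognises speech poorly or that the words were never audible, and the score alone cannot say which. Scores would also not be comparable between hearing groups, because each group would hear the words at a different distance above threshold.

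**Working it through.** There is no sample size, power or effect figure to reproduce here. The check is whether the stated level has the stated property.

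**Inputs from the Protocol**
- Word level: 60 dB HL (Study Design and Methods).
- Hearing-impaired participants in Phase 2: 15 + 15 = 30 (Second phase clinical trial, item 1).
- Upper limit on hearing loss: none (Subject Information).
- Thresholds: measured by frequency from 250 Hz to 20 kHz, before word testing. The protocol mentions no separate speech threshold.

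**Assumption.** The documents give no participant thresholds, so a range of speech thresholds T is used.

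**Formula.** Level above threshold = 60 - T. The words are suprathreshold only if this is greater than 0.

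| Assumed threshold T (dB HL) | 60 - T (dB) | Suprathreshold? |
|---|---|---|
| 0 | +60 | yes |
| 25 | +35 | yes |
| 40 | +20 | yes |
| 50 | +10 | yes, by a small margin |
| 60 | 0 | no, at threshold |
| 70 | -10 | no |
| 90 | -30 | no |

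For normal-hearing listeners the label holds with room to spare. The masking noise used in Phase 2 to simulate loss in normal-hearing participants reaches 50 dB HL. If it raised threshold to its own level (an assumption), 60 dB HL would still be 10 dB above.

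For hearing-impaired ears the label fails from T = 60 dB HL upward. Eligibility allows such ears, and the deaf ear of a person with single-sided deafness would be expected to be one.

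**What cannot be computed.** The number of affected ears needs a distribution of thresholds and a statement of which ear is tested, and the protocol gives neither. The 30 participants are an upper bound on the people concerned, not an estimate. A shift in group mean scores cannot be given either, because even the floor is uncertain. It would be near 0% for open-response words. For the Modified Rhyme Test scored as a six-alternative choice it would be about 1/6 = 16.7%. The Phase 2 text says only "word recognition using a standard work recognition test" and does not say which test that is.

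**The case against.** The strongest reply is that word recognition is not the main purpose in the hearing-impaired groups. Item 1 of the Second phase recruits them to assess directionality. The explicit comparison with acoustic threshold and speech measures appears in item 2, which concerns normal-hearing participants with simulated loss. The Second phase text does not repeat 60 dB HL. The only numeric speech target, above 90% in quiet, is for normal hearing, and the endpoints are working headsets. All of this is correct and limits how much depends on the point. It does not remove it: word recognition is still listed for Phase 2 participants, Key Objectives item 6 names it for the hearing-impaired groups, and the general Methods supply the only level available. If another level was intended, the protocol needs to say so.

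It is also fair to say that an asymmetrical participant has a better ear, and that testing that ear, or both ears together, could keep words audible. The tested ear is not stated, so this may or may not happen, and it gives no assurance for the 15 bilateral participants.

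A reader might go further and infer that the electrical system would look better than conventional sound, because current is raised until the signal is heard. The documents do not support that. Raising the current until something is heard is described for tone thresholds (Lateralization and Third phase clinical trial), not for words, and the electrical word level is not given. The Phase 2 masking work aims to predict electrical thresholds from air-conduction thresholds, so the protocol expects the two to be related, and low scores on both sides are possible. Nor should all 30 hearing-impaired participants (or the 40 implied by Key Objectives item 6) be counted as affected, since words stay above threshold in any ear better than 60 dB HL.

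Finally, whether to test at a common level or at an equal distance above threshold depends on the question, since audibility can be part of a device's benefit. That is a reason to report inaudible ears openly, not to leave them unidentified among low scores.

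**Conclusion.** The point holds as an internal inconsistency with a practical consequence. The protocol calls 60 dB HL suprathreshold for everyone, yet its own eligibility rules admit ears for which this is false, namely any tested ear with a threshold of 60 dB HL or worse. In those ears a low acoustic score does not separate poor recognition from inaudible words. Between about 40 and 55 dB HL the label is true but the margin is only 20 to 5 dB, so scores remain hard to compare with those of normal-hearing listeners.

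The conclusion assumes that the general Methods level carries over to Phase 2, since no other is given, and that some enrolled hearing-impaired ears are tested at or beyond that threshold. The number of such ears is unknown, and neither the size nor the direction of any bias in the electrical-versus-acoustic comparison can be established from the document. The normal-hearing cohorts are not affected. A test level is a matter of procedure that the protocol has itself fixed, so this is not a detail that can be presumed to sit in an analysis plan.

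**What to change.** Reconcile the fixed level with the word suprathreshold for the Phase 2 hearing-impaired groups:

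- Keep 60 dB HL for the normal-hearing cohorts.
- For hearing-impaired participants, name the tested ear and set the acoustic word level relative to that ear's measured thresholds. Because thresholds are taken by frequency, state which summary of the speech-frequency thresholds serves as the reference, and stay within the audiometer's usual limits.
- Record the level above threshold alongside every word score.
- Where words cannot be made suprathreshold, report the ear as not testable acoustically instead of as a low recognition score, and give the number of such ears.
- Show the electrical-versus-acoustic comparison with these ears identified, so that any effect of setting them apart is visible. They may include the deaf ears that the device is meant to serve.

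The cost is a short change to the Methods, a definition of the reference threshold and a per-ear level setting. Thresholds are already measured first, so no further pure-tone testing is needed. The drawback is small: presentation levels will differ between participants, and some ears will give no acoustic score.
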